# **AirFLO2 Treatment for Hypoxia and/or Tachypnea in Patients with COVID-19**

## **Research Protocol**

**Version 3 – 21SEP2020**

**NCT04649775**

## Study Summary

Title	AirFLO2 Treatment for Hypoxia and/or Tachypnea in Patients with COVID-19
Short Title	AirFLO2 with COVID-19
IRB Protocol number	Pro00105246
Study Center	Duke
Study Aims	
Primary:  Determine if use of the AirFLO2 device will reduce hypoxia in patients admitted to the hospital with COVID-19 infection. The aim of our study is to determine whether the use of the AirFLO2 device can improve hypoxia as measured by change between baseline P:F ratio and repeat P:F ratio between 1 to 6 hours after using the device.
 
Secondary:  Determine if use of the AirFLO2 device will
 
 
a) Improve subjective symptoms related to dyspnea and comfort
 
b) reduce risk of progression to high flow nasal cannula (HFNC), non-invasive ventilation (NIV), or invasive ventilation
 
c) reduce intensive care unit (ICU) transfer risk
 
d) reduce intubation risk
 
e) reduce days of hospitalization
 
f) increase survival to discharge
 

Number of Subjects	A targeted sample size of 46 subjects will be required, with an expected dropout rate of 10%, a total sample size of 50 subjects will be necessary to complete the study.
Inclusion Criteria	
 
• Adults <math>\geq 18</math> years of age with confirmed COVID-19 infection
 
• Patient must be able to complete consent and hold mask
 
• Baseline room air oxygen saturation <math></= 94\%</math> or patient with new supplemental oxygen requirement at presentation or patient on supplemental oxygen at baseline and requiring up-titration of oxygen setting
 
 Patient must have access to an internet-connected device
Exclusion Criteria	
 
• Tracheostomy
 
• History of pneumothorax or known bullous lung disease
 
• Recent cataract surgery
 
• Patient receiving NIV (Noninvasive Ventilation) or HFNC (High Flow Nasal Cannula)
 
• Patient receiving mechanical ventilation
 
• Active TB
 
• Seizures
 

		
 
• Delirium
 
											
Study Schedule		
Following prescreening for eligibility, participants will provide consent. It is expected the primary consent will be performed at the in-patient bedside with a study coordinator to facilitate and answer questions.
 
After consent, baseline clinical data will be recorded and study related parameters post consent will be collected
											

Parameter	1 hr pre	baseline	1 hr	2 hr	4 hr	6 hr	8 hr	12 hr	Every 24 hr	discharge	withdraw	death
Sp02	X	X	X	X	X		X	X	X	X		X
ABG	X	X	X	X	X		X	X	X	X		X
P/F	X	X	X	X	X		X	X	X	X		X
NC L/m	X	X	X	X	X		X	X	X	X	X	X
HFNC			Yes /No	Yes /No	Yes /No		Yes /No	Yes /No	Yes /No	Yes /No	Yes /No	Yes /No
NIV			Yes /No	Yes /No	Yes /No		Yes /No	Yes /No	Yes /No	Yes /No	Yes /No	Yes /No
Ventilator free			Yes /No	Yes /No	Yes /No		Yes /No	Yes /No	Yes /No	Yes /No	Yes /No	Yes /No
Roth scale		X								X		
CV		X	(betw een	1 & 6hrs)						X		
LCQ		X	(betw een	1 & 6hrs)						X		
SOFA score		X										
Platelet		X										
Creatinine		X										
MAP		X										
Vasopressor tx		X										
Vasopressor dose		X										
Bilirubin		X										
Glasgow coma scale		X										
COVID-19 inflamm		X										

atory markers											
D-Dimer		X									
Ferritin		X									
CRP		X									
Creatine kinase		X									

### **Primary objective:**

Determine if use of the AirFLO2 device will reduce hypoxia in patients admitted to the hospital with COVID-19 infection. The aim of our study is to determine whether the use of the AirFLO2 device can improve hypoxia as measured by change between baseline PaO2:FiO2 ratio and repeat PaO2:FiO2 ratio between 1 to 6 hours after using the device.

### **Secondary Objectives:**

Determine if use of the AirFLO2 device will

- g) Improve subjective symptoms related to dyspnea and comfort
- h) reduce risk of progression to high flow nasal cannula (HFNC), non-invasive ventilation (NIV), or invasive ventilation
- i) reduce intensive care unit (ICU) transfer risk
- j) reduce intubation risk
- k) reduce days of hospitalization
- l) increase survival to discharge

### **Background and Significance:**

The coronavirus disease 2019 (COVID-19) outbreak that started in Wuhan, China in December 2019 has now extended across the globe with > 1 million cases world-wide and 52,863 deaths as of April 1, 2020 (Johns Hopkins data). In North Carolina, 2016 cases have thus far been identified with 24 deaths and 184 admitted to hospitals in the state. These numbers are rapidly rising. In patients admitted with acute viral infection due to COVID-19, traditional methods to treat respiratory failure with non-invasive positive pressure ventilation are often being bypassed for fear of aerosolization of virus resulting in presumptive intubation for COVID-19 and a shortage of ventilators (PMID: 32212516). There is an urgent need to identify interventions which can retard or block progression to ARDS and reduce the need for invasive ventilation.

In adults with COVID-19 at risk for respiratory failure, the addition of conventional oxygen is recommended for O2 saturations <=94%. If hypoxemia progresses, the Surviving Sepsis Campaign recommends using high flow nasal cannula over conventional oxygen therapy and a high PEEP strategy in the management of ARDS (PMID:32222812).

### **Methods:**

We propose an innovative device that can provide a low-cost, non-invasive, portable method to provide positive end expiratory pressure to improve oxygenation by decreasing respiratory muscle work of breathing, decreasing atelectasis, and increasing functional residual capacity (PMID: 23115688). Our novel device (**Figure 1**) features a mask, an adjustable pressure (5-20cm H2O) outflow valve to meet individual patients' needs and an inflow valve to allow for free-flowing inhalation. If short of breath, the patient will apply the AirFLO2™ mask over their nose and mouth, forming an air-tight seal. The patient can breathe through the outflow valve; the valve will create positive pressure within the mask according to the

adjustable pressure setting. The pressure provided by the mask helps to reduce atelectasis and recruit alveoli to reduce ventilation-perfusion mismatch. By leveraging well established technologies, we have created an accessible device with a low barrier for training and adoption. In addition, it can easily be decontaminated by removing the valve, wiping down and performing a simple at-home washing protocol with soap and water.

### **Design & Procedures:**

We propose an unblinded, randomized, controlled trial for use of the AirFIO2 device for patients admitted to Duke Hospital with COVID-19 and tachypnea (RR >20 breaths/min) and/or hypoxia (Oxygen saturation </=94% on room air or requiring supplemental oxygen at baseline).

#### **Inclusion criteria:**

- Adults  $\geq 18$  years of age with confirmed COVID-19 infection
- Patient must be able to complete consent and hold mask
- Room air oxygen saturation </=94%, patient with new supplemental oxygen requirement, or patient on supplemental oxygen at baseline and requiring up-titration of oxygen setting
- Patient must have access to an internet-connected device

#### **Exclusion criteria:**

- Tracheostomy (current)
- History of pneumothorax or known bullous lung disease
- Recent cataract surgery
- Patient receiving NIV (Noninvasive Ventilation) or HFNC (High Flow Nasal Cannula)
- Patient receiving mechanical ventilation
- Active TB
- Seizures
- Delirium preventing patient from providing informed consent or self-applying mask

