#### **Study groups:**

We will enroll n=50 patients with hypoxia (O2 saturation 90% or less on RA) and use clinical data including:

- Room air oxygen saturation
- PaO2/FiO2 ratio 1 hour prior to and then 1, 2, 4, 8, 12 and every 24hours after using AirFIO2.
  - If arterial blood gas result is not available for any time point then the P:F ratio will be imputed using the SpO2.
  - If the patient is on nasal cannula, the estimated FiO2 delivery will be calculated based on the oxygen flow rate in liters per minute (LPM).
- Transition to HFNC or NIV
- ICU transfer
- Ventilator free days
- Survival to discharge
- Cardiovascular (CV) Questionnaire, Cough questionnaire, and Roth score will be completed at baseline, and before discharge by all consented participants and the two questionnaires repeated 1-6 hours after using the device for subjects randomized to receive the AirFIO2.

Additional clinical data pertaining to overall disease severity as measured by the Sequential Organ Function Assessment (SOFA) score and inflammatory markers related to COVID-19 infection will be collected:

- SOFA score
  - Platelet count

- Creatinine
- Mean arterial pressure
- Vasopressor treatment and dose
- Bilirubin
- Glasgow Coma Score (extracted from clinical documentation)
- COVID-19 inflammatory markers
  - D-dimer
  - Ferritin
  - C reactive protein (CRP)
  - Creatine kinase
  - Lymphocyte percentage

These clinical data will be obtained via chart review. For each lab value, the collection time point nearest to study enrollment will be recorded.

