### **Intervention**

Intervention subjects will receive the AirFLO2 device and training via video with reinforcement from the coordinator how to use and to self-apply it. Bedside nurses will also be given instructions, access to the study video and verbal training as well, so that they can answer simple questions for the patients.

Initially the CRC will hand device to the patient. Oxygen saturation at baseline will be recorded. The patient will set the PEEP at 5 on the mask, then hold the mask firmly against the face, take a full slow deep breath in, then exhale steadily out until out of breath. Record oxygen saturation. Wait 3-5 minutes then repeat maneuver with PEEP at 10. Record oxygen saturation. Repeat again with PEEP at a setting of 15, then again at 20. The highest O2 saturation achieved with the lowest PEEP is the PEEP setting to use. If oxygen saturation does not change or decreases, leave at PEEP of 5.

All other elements of patient care will be managed by the treating physician(s).

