### **Data Analysis & Statistical Considerations**

Sample size calculation was performed, assuming a hypothesized increase in P:F ratio of +25 in the intervention group, no change in P:F ratio in the control group, and standard deviation of 30 in both groups. With these assumptions, for statistical power of 80%, a sample size of 46 subjects will be required. With an expected dropout rate of 10%, a sample size of 50 subjects will be necessary to complete the study.

Groups will be analyzed by intention to treat. Per-protocol analyses will also be performed.

Descriptive statistics will be reported for the overall subject population, and for the two groups.

The primary outcome of intra-subject change in P:F ratio before and after using the device will be analyzed with a paired student's t-test. The absolute change and percent change in P:F ratio will be compared between the control and intervention groups with student's t-tests. A multivariate analysis will be performed comparing the change in P:F ratio using linear regression, controlling for baseline P:F ratio, baseline overall disease severity (SOFA), and baseline COVID-19 related disease activity markers.

Secondary outcomes of risk for high flow nasal cannula, noninvasive ventilation, invasive ventilation will be compared between the intervention and control groups with the  $\chi^2$ -squared test. Survival to discharge will be compared with the  $\chi^2$ -squared test. Logistic regression analysis will be performed for each of these outcomes, controlling for baseline P:F ratio, baseline overall disease severity (SOFA), and baseline COVID-19 related disease activity markers.

Ventilator-free days will be compared using the student's t-test for bivariate analysis, and linear regression for multivariate analysis, controlling for baseline P:F ratio, baseline overall disease severity (SOFA), and baseline COVID-19 related disease activity markers.

Secondary outcomes of questionnaires related to subject symptoms before and after using the device will be analyzed for intra-subject change in questionnaire scores using paired student's t-tests. A multivariate analysis will be performed comparing the change in questionnaire scores using linear regression, controlling for baseline questionnaire score, baseline P:F ratio, baseline overall disease severity (SOFA), and baseline COVID-19 related disease activity markers.

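### The plan specifies no adverse-event or device-event collection and no safety analysis in either arm, so device-specific harms such as pneumothorax would not be captured systematically

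*Combined protocol and SAP*

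**What the plan says.** - **Device (Methods).** The mask has "an adjustable pressure (5-20cm H 2 O) outflow valve". It is applied by the patient when short of breath and, under Subject Recruitment and Compensation, is collected at hospital discharge. Use can therefore continue well beyond the coordinator-supervised first session.
- **Exclusion criteria.** These include "History of pneumothorax or known bullous lung disease" and "Recent cataract surgery". No reason is given for either.
- **Intervention.** Saturation is recorded at baseline and as the pressure is stepped up. The section allows for a fall: "If oxygen saturation does not change or decreases, leave at PEEP of 5".
- **Study Schedule and Study groups.** The items cover oxygenation, respiratory support, questionnaires, SOFA components and inflammatory markers; ICU transfer and survival appear in the Study groups list. On the source, the list says "These clinical data will be obtained via chart review". There is no entry for adverse events, serious adverse events, pneumothorax, other barotrauma or device problems. The withdrawal column carries respiratory-support items but no reason for withdrawal.
- **Objectives and Data Analysis & Statistical Considerations.** There is no safety objective and no safety analysis. Two groups of outcomes that bear on harm are compared between arms: "Secondary outcomes of risk for high flow nasal cannula, noninvasive ventilation, invasive ventilation will be compared between the intervention and control groups" and, separately, "Survival to discharge will be compared with the" chi-squared test. ICU transfer is an objective ("reduce intensive care unit (ICU) transfer risk"), but no test is named for it.

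**The concern.** A device that holds positive pressure in the airway can plausibly do harm of its own, and pneumothorax is the obvious candidate. An oxygenation gain on the primary outcome has to be weighed against such harm, and that requires harm to be counted in the same way in both arms. The trial is unblinded, so events noticed informally at the bedside are likely to be noted more readily in the device arm. Without defined fields for both arms, any safety statement in the report would rest on incomplete and possibly unequal ascertainment.

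**Working it through.** **1. What the plan as written would show for each kind of event**

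| Event | Trace under the current plan |
|---|---|
| Death | Recorded; survival to discharge compared between arms |
| Pneumothorax leading to intubation | Counted as invasive ventilation; not separable from COVID-19 progression |
| Pneumothorax without escalation, ICU transfer or death | No event recorded; at most a change in a scheduled SpO2 or P:F value |
| Device stopped because of a problem | No item; if the patient also withdraws, a withdrawal without a reason |
| Saturation fall in the stepwise session | Recorded under Intervention, but with no column in the schedule, no entry in the data list and no analysis |

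The second to fourth rows are the gap. The last row is narrower: the reading is taken, but the plan gives it no data field and no use.

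**2. Number of device patients**

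Inputs from Data Analysis & Statistical Considerations: difference 25, SD 30, power 80%. Two-sided alpha 0.05 and 1:1 allocation are assumed, because neither is stated.

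- n per arm = 2 × (1.96 + 0.842)² × 30² / 25² = 2 × 7.85 × 1.44 = 22.6, rounded up to 23. The total is 46, as the plan states.
- Dropout: 46 / 0.90 = 51.1, or 52 in two equal arms. The plan states 50; the difference does not matter here.
- Under 1:1, this means 25 device patients enrolled and 23 evaluable.

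**3. What recording could establish if no event of a given type occurred**

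The exact upper limit U solves (1 − U)^n = a, so U = 1 − a^(1/n).

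| n | Two-sided 95% (a = 0.025) | One-sided 95% (a = 0.05) |
|---|---|---|
| 25 | 1 − 0.025^(1/25) = 13.7% | 1 − 0.05^(1/25) = 11.3% |
| 23 | 1 − 0.025^(1/23) = 14.8% | 1 − 0.05^(1/23) = 12.2% |

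**4. Chance of seeing at least one event among 25 device patients**

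This is 1 − (1 − p)^25. The documents give no event rate, so a range is assumed: 22% at p = 1%, 40% at 2%, 72% at 5% and 93% at 10%.

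Systematic recording would probably reveal a common device harm (5% or more). It could neither reliably show nor exclude one at 1% to 2%.

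**The case against.** A reader might infer that the trial collects no harm data and can say nothing about device safety. The documents do not support that. Death, HFNC, NIV, invasive ventilation, ventilator-free days, ICU transfer and serial SpO2 and P:F are all collected. The analysis section compares survival and respiratory escalation between arms, and its tests name no direction, so excess deaths or intubations on the device would be visible, if imprecisely. Nor is it true that no event rate could be bounded: for death and intubation it could.

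Three further readings go too far:

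- **That the stepwise saturations go unrecorded.** The Intervention section orders them to be recorded and chooses the setting from them. Only the data field and the analysis are missing.
- **That the exclusions prove the sponsor foresaw pressure injury.** This is plausible for a pressure device, but no reason is stated, so it remains an inference. The point does not depend on it.
- **That no reporting of events exists anywhere.** Consent pages were removed from the text, and reporting duties may sit outside it. The schedule, data list and analysis section are present, however, and those are where by-arm collection and analysis would be specified. Reporting single events to a review board would not by itself yield a comparable dataset for the two arms.

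It is also fair to say that a trial of 50 can support little about safety even with full recording. That limits what the fix can deliver, but it does not justify leaving the events uncounted.

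**Conclusion.** The point holds as an omission in collection and analysis. Device-specific harms, pneumothorax above all, would not be captured systematically and could not be separated from disease progression. Mortality, respiratory escalation, ICU transfer and SpO2 remain as indirect evidence. The omission does not affect the primary P:F comparison; it affects whether a gain there can be set against harm. With recording in place, 0/25 would exclude a true risk above 13.7% (exact two-sided 95%; 11.3% one-sided), so only limited safety statements would be possible. The bound assumes 1:1 allocation and follow-up of all 25 device patients; with 23 it is 14.8% (12.2% one-sided).

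**What to change.** 1. **Both arms, identically, from randomisation to discharge.** Add to the Study Schedule and to the chart review under Study groups: new pneumothorax or other barotrauma, serious adverse events with a definition, and the reason for any withdrawal.
2. **Device arm only.** Add device discontinuation with its reason, which has no counterpart under usual care and should not enter the between-arm comparison. Add a data field for the stepwise saturations that the Intervention section already has recorded.
3. **Data Analysis & Statistical Considerations.** Add one table of events by randomised arm, and again by treatment received, with exact two-sided 95% confidence intervals. State that the sample allows only limited conclusions on safety.

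The cost is a few fields, one table and some abstraction time, since chart review is already the data source. Nothing in this changes a pressure setting or any rule of clinical management.

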#### **Study groups:**

We will enroll n=50 patients with hypoxia (O2 saturation 90% or less on RA) and use clinical data including:

- Room air oxygen saturation
- PaO2/FiO2 ratio 1 hour prior to and then 1, 2, 4, 8, 12 and every 24hours after using AirFIO2.
  - If arterial blood gas result is not available for any time point then the P:F ratio will be imputed using the SpO2.
  - If the patient is on nasal cannula, the estimated FiO2 delivery will be calculated based on the oxygen flow rate in liters per minute (LPM).
- Transition to HFNC or NIV
- ICU transfer
- Ventilator free days
- Survival to discharge
- Cardiovascular (CV) Questionnaire, Cough questionnaire, and Roth score will be completed at baseline, and before discharge by all consented participants and the two questionnaires repeated 1-6 hours after using the device for subjects randomized to receive the AirFIO2.

Additional clinical data pertaining to overall disease severity as measured by the Sequential Organ Function Assessment (SOFA) score and inflammatory markers related to COVID-19 infection will be collected:

- SOFA score
  - Platelet count

- Creatinine
- Mean arterial pressure
- Vasopressor treatment and dose
- Bilirubin
- Glasgow Coma Score (extracted from clinical documentation)
- COVID-19 inflammatory markers
  - D-dimer
  - Ferritin
  - C reactive protein (CRP)
  - Creatine kinase
  - Lymphocyte percentage

These clinical data will be obtained via chart review. For each lab value, the collection time point nearest to study enrollment will be recorded.

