### **Control**

Control subjects will receive usual care, managed by the treating physician(s).

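### The primary P:F change is timed from device use, which gives the two arms no common clock; no reading in the 1–6 h window is designated, and the primary outcome is tied to a paired test

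*Combined protocol and SAP*

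**What the plan says.** The Study Summary defines the primary outcome as the "change between baseline P:F ratio and repeat P:F ratio between 1 to 6 hours after using the device", and the Primary objective repeats this ("ratio between 1 to 6 hours after using the device"). The Study groups section schedules P:F "1 hour prior to and then 1, 2, 4, 8, 12 and every 24hours after using" the device. The Data Analysis section calls it the "primary outcome of intra-subject change in P:F ratio before and after using the device" and assigns it a paired t-test. It then says that the absolute and percent "change in P:F ratio will be compared between the control and intervention groups" by t-test, and that "Groups will be analyzed by intention to treat", with per-protocol analyses in addition.

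Under Control, patients receive usual care only. Under Methods, the mask is applied when the patient is short of breath. Under Intervention, there is a coordinator-supported first session, which is not named as hour zero. The Study Schedule grid has a column one hour before, a separate baseline column and hourly columns. It follows a sentence about collection after consent but does not define hour zero. Randomisation also follows consent; its order relative to the baseline reading is not given.

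**The concern.** A randomised comparison needs both arms read on the same clock. Here the clock starts at an event that controls do not have, that some device-arm patients might not have, and that others may have several times. Someone must supply an index time later, in an unblinded trial.

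Two further choices are open. The window holds three readings with no rule for picking or combining them. The Study groups section lists only the reading one hour before, while the grid lists that reading and a baseline.

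The test attached to the primary outcome is also not the randomised contrast. A paired test shows whether P:F moved over a few hours, which usual care, natural course or regression to the mean can produce without any device effect. Two competent analysts could therefore report different primary results from the same data.

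**Working it through.** **1. The plan's sample size.** Inputs from the Data Analysis section: +25 v 0, SD 30, power 80%. Two-sided 5% and 1:1 allocation are assumed, because neither is stated. Per arm, n = 2 × (1.96 + 0.8416)² × 30²/25² = 2 × 7.849 × 1.44 = 22.6, so 23 per arm and 46 in total, as stated. Power at 23 per arm is 80.7% by the normal approximation and 78.9% by the noncentral t. A paired test of +25 in one group would need half of 22.6, that is 11.3 or 12 patients. The figure of 46 therefore belongs to the two-group comparison, while the paired test is the one attached to the primary outcome.

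**2. Time zero, by section.**

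| Section | Anchor | Applies to controls? |
|---|---|---|
| Study Summary, Primary objective | after device use | no |
| Study groups | before and after device use | no |
| Data Analysis, paired test | before and after device use | no |
| Data Analysis, between-arm test | none stated | needs one |
| Study Schedule grid | after consent; hour zero undefined | possibly |

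**3. Readings in the window.** P:F is scheduled at 1, 2 and 4 h. The 6 h cell of the grid is blank and the Study groups list has no 6 h reading, so there are three candidates.

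**4. Cost of leaving the reading open (illustration; the plan states no such rule).** No true effect, 23 per arm, equal correlation r between the three changes, success declared if any of three t-tests has p < 0.05. With 200,000 simulated trials per setting:

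| r | False positives |
|---|---|
| 0.9 | 8.3% |
| 0.7 | 11.0% |
| 0.5 | 12.7% |

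Independent readings would give 1 − 0.95³ = 14.3%.

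**5. Power once the clock starts at randomisation.** SD 30 is taken as the SD of change at one reading. The mean of three has SD 30√((1 + 2r)/3) = 29.0, 26.8 and 24.5 for r = 0.9, 0.7 and 0.5. With a constant effect of 25, its power is 82%, 87% and 92%, against 79% for a single reading.

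Now let a fraction f of the device arm start late, with full effect from the next reading on.
- Mean, start between 1 and 2 h: effect 25(1 − f/3); add f(1 − f)(25/3)² to the device-arm variance.
- Mean, start between 2 and 4 h: effect 25(1 − 2f/3); add f(1 − f)(50/3)².
- Either summary, start after 4 h or never: effect 25(1 − f); add f(1 − f)25².

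Power in % (ranges run over r = 0.9 to 0.5):

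| f | Mean, start 1–2 h | Mean, start 2–4 h | Mean, after 4 h or never | 4 h alone, start before 4 h | 4 h alone, after 4 h or never |
|---|---|---|---|---|---|
| 10% | 79–90 | 76–88 | 72–85 | 79 | 69 |
| 25% | 74–87 | 65–79 | 55–68 | 79 | 52 |
| 50% | 66–80 | 46–59 | 28–36 | 79 | 26 |

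The documents give no late-use or non-use rate; every f is an assumption.

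**The case against.** The best defence is that a common schedule is the natural reading. P:F is listed for all 50 patients and the grid is not split by arm. Where the authors mean device-arm only they say so: "two questionnaires repeated 1-6 hours after using the device for subjects randomized to receive the AirFIO2". That restriction on the questionnaires suggests that P:F is for everyone, and a reader should not infer that controls go unmeasured. What stands against the defence is that the grid does not define hour zero and that four sections say after use. The defence also leaves the choice of reading and the paired test untouched.

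Two stronger readings are tempting, and the documents do not support them.

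- A reader might infer that non-users will be left out for want of a time zero, which would favour the device. That would breach the plan's own intention-to-treat rule. If it happened, and non-users' change were 30 points worse (assumed), device-favouring false positives would rise from 2.5% to about 3% at 2% non-use, 3.7% at 5%, 5% at 10% and 8% at 20%. The supervised first session, and the requirement that patients can hold the mask, make the high end unlikely.
- A reader might infer a free choice between two baselines, doubling the number of tests. The grid has a distinct baseline column, the objective names a baseline and the regression adjusts for baseline P:F. The Study groups list is inconsistent with these, but that is not an open choice.

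**Conclusion.** The point holds as a defect of definition in the primary outcome, and it should be corrected before outcome data are compared. The stated time zero cannot be applied to controls and is not unique for users. The reading is undesignated, and the test attached to the primary outcome is not the one the sample size supports. The between-arm comparison is in the plan; it lacks a clock and primary status.

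The undesignated reading could raise a nominal 5% error to about 8–13%. That rests on 23 per arm, a two-sided 5% level, equal correlations of 0.9 to 0.5, and an analyst who accepts any of the three readings. The sample size arithmetic is not affected.

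**What to change.** - Start the clock at randomisation in both arms, in a fixed order: baseline P:F, randomisation, then device handover shortly after. Define baseline as the last P:F before randomisation, and align the Study groups list with the grid.
- Name one primary summary before any outcome data are compared, for example the mean of the 1, 2 and 4 h values. State a rule for missing readings and for how P:F is analysed when support is escalated within the window.
- Make the between-arm comparison of change, in all randomised patients whether or not they used the device, the primary test. Keep the paired test as descriptive only.

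The cost is wording plus a fixed order of three steps, with no new measurements and no change in the number of patients. The price is dilution by late use or non-use, as tabulated above.

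The mean is also a trade-off. If the effect fades (25, 16.7, 8.3 at 1, 2 and 4 h), its average is 16.7 and the mean has 48–62% power against 15% for 4 h alone. If it builds in the reverse order, the mean has 48–62% against 79%. The documents give no time course, so the choice should be made on clinical grounds and written down.

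Switching between blood gas and SpO2-imputed P:F within a patient is a separate matter, best handled by a sensitivity analysis.
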